3C4b. Assessment: Lay Counselors. In addition to clinical outcomes, we examine implementation factors that may affect clinical outcomes and, by measuring them in this RCT, we establish a benchmark for future implementation efforts. Implementation outcomes, as detailed below, include child and guardian attendance at groups (which may vary across countries; urban vs. rural settings), lay counselors' knowledge and fidelity to TF-CBT, and the lay counselor-supervisor relationship. Lay counselors will complete measures assessing knowledge and the supervisory relationship with the local trainers (see Table 4). These measures are administered to the lay counselors by the project coordinator (PC) in each site via paper and pencil self-report format and will be returned to the PC in a sealed envelope. Self-report fidelity data will involve lay counselors completing the group reports after each TF-CBT group session and emailing these reports to the local trainers and to [name] and [name], within two days of the group. Lay counselors audiorecord all sessions digitally. The electronic files are collected by the PC on a jump drive. Three child and 3 guardian sessions (6 total) will be randomly selected from each group by [name] (remotely) and will then be coded by the data entry person, who also serves as the independent coder and will be trained by Drs [name] and Cohen in TF-CBT coding procedures.

3C4c. Data Collection from Children and Guardians. As in our other research, interviewers who have experience in working with children and a college degree in a field related to data management or social services are selected. Interviewers will undergo one week of training. Interviewers receive training in issues of research confidentiality, protocols, ensuring common understanding of questions, and standard ethical procedures (see Human Subjects for more information and Appendix C for example training documents). Interviewers will not be allowed to begin interviewing until they have been certified by [name] and [name] on all procedures and passed practice interviews (see Appendix C: Interview Training Log).

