These aims would be tested by adding country and rural or urban setting as predictors at Level 2. These analyses would test whether country or setting explain between-condition differences in treatment outcomes at

a specific time point, and for the growth models, whether they explain differences between conditions in the rate of change over time.

Aim 3. Examine the impact of implementation factors (e.g., TF-CBT fidelity, lay counselor-supervisor relationship, child/guardian attendance) on outcomes.

Analyses for Aim 3 will focus on how implementation variables (such as attendance, fidelity, provider knowledge) are related to outcomes at 12-14 weeks (end of TF-CBT) and at the follow-ups. These analyses will be restricted to those in the TF-CBT condition. These Aims are tested by expanding the models described in Aims 1 and 2, above, to include implementation variables at both the individual level (such as attendance) and the group level (TF-CBT fidelity). For example, MLM equations that look at implementation effects on post-treatment levels of symptoms could be:

Level 1:	$Symptoms_{ig} = B_{0g} + B_{1g}PreSx + B_{2g}Cov + B_{3g}Attendance + e_{ig}$
Level 2:	$B_{0g} = \pi_{00} + \pi_{01}Fidelity + r_0$ $B_{1g} = \pi_{30}$ $B_{2g} = \pi_{30}$ $B_{3g} = \pi_{30} + r_2$

These models test how attendance during treatment and fidelity of the treatment provider influence symptoms at 12-weeks and at follow-ups, treating the intercept and the effects of attendance as random effects, and the

effects of pre-treatment symptoms and covariates as fixed effects.

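### The example Aim 3 model gives attendance one uncentred slope, so its individual-level coefficient mixes within-group and between-group associations and can show an individual effect where none exists

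*Combined protocol and SAP*

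**What the plan says.** Aim 3 (section 3C5b) asks how implementation variables relate to outcomes, using the TF-CBT arm only: "These analyses will be restricted to those in the TF-CBT condition". It places attendance at the individual level and fidelity at the group level, with models that "include implementation variables at both the individual level (such as attendance) and the group level (TF-CBT fidelity".

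The equations are introduced as an illustration: "MLM equations that look at implementation effects on post-treatment levels of symptoms could be". In them:

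- Level 1 contains "B_{3g}Attendance + e_{ig}", with no centring shown.
- The Level 2 intercept contains "\pi_{01}Fidelity + r_0", so Fidelity is the only group-level predictor displayed.
- Attendance has one average slope with a random deviation; the text describes "treating the intercept and the effects of attendance as random effects".

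Two other statements bear on the point. Section 3C4b lists among the implementation outcomes "child and guardian attendance at groups (which may vary across countries; urban vs. rural settings", so between-group variation in attendance is foreseen. Aim 3 also says "These Aims are tested by expanding the models described in Aims 1 and 2, above", and the Aim 2 model adds country and urban or rural setting at Level 2. The document does not mention centring, group-mean attendance, or separate within-group and between-group slopes.

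**The concern.** Each child belongs to one TF-CBT group, so attendance varies both among children within a group and between groups. A mixed model with one slope for uncentred attendance assumes that the two associations are equal and averages them by precision. If groups that attend better also have lower symptoms for group-level reasons, part of that difference enters the attendance coefficient. It would then be read as the effect of a child attending more sessions.

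The distinction matters here because the plan assigns attendance to the individual level and fidelity to the group level. Section 3C5c rests on the same split: it claims good power for individual-level variables and little for group-level ones. A false individual-level finding could misdirect later implementation work towards individual attendance when the difference lies between groups.

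**Working it through.** **Plan's own figure.** Section 3C5c gives .21 as the detectable effect of an individual implementation variable with 320 children. Its scale and ICC are not stated. Read as a correlation, power at N = 320 is .967 without clustering. With design effect 1 + (8 - 1) x ICC it is .827 at ICC .10 and .751 at ICC .15. Read as a standardised difference, power is .467. The figure can be neither reproduced nor refuted, and the point does not depend on it.

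**Inputs from the plan.** 8 children per group; 20 TF-CBT groups per region (section 3C2), so 320/8 = 40 groups; alpha .05, taken as two-sided.

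**Assumed, because the documents give no value.** Attendance ICC (ICCx) .2 to .3; residual outcome ICC (ICCy) .05 to .10; group-level slope -0.5 SD of outcome per SD of attendance; true within-group effect zero.

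**Weights in a random-intercept model, n = 8.**

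- Within-group information: W = (n - 1)(1 - ICCx)/(1 - ICCy).
- Between-group information: B = n[ICCx + (1 - ICCx)/n] / [(1 - ICCy) + n x V], where V is the intercept variance in the fitted model.
- Group-mean reliability: R = ICCx / [ICCx + (1 - ICCx)/n].
- Expected slope: b = -0.5 x R x B/(W + B). SE = 1/sqrt[40(W + B)].

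The fitted intercept also absorbs the group effect that the single slope misses, so V is approximately ICCy + (0.5 - |b|)^2 x ICCx, solved together with b.

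*Low case (ICCx .2, ICCy .10).* W = 7 x .8/.9 = 6.222. V = .10 + (.4465)^2 x .2 = .140. B = 2.4/(.9 + 8 x .140) = 1.19. R = .2/.3 = .667. b = -0.5 x .667 x 1.19/7.41 = -.053. SE = .058. Rejection is about 15%.

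*High case (ICCx .3, ICCy .05).* W = 7 x .7/.95 = 5.158. V = .05 + (.400)^2 x .3 = .098. B = 3.1/(.95 + 8 x .098) = 1.79. R = .3/.3875 = .774. b = -0.5 x .774 x 1.79/6.95 = -.100. SE = .060. Rejection is about 38%.

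Simulation of the same settings (REML, random intercept) gave 15% and 18% in two runs for the low case, and 37% and 38% for the high case, with mean slope about -.096 in the latter. At attendance ICC .05 the rate is about 6%.

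**Keeping country and setting in the model (simulation, residual outcome ICC .10, attendance ICC .2 to .3).** If they explain all group variation in attendance, rejection is about 4-5%. If they explain half, it is about 9-12%. If .10 is instead read as the total outcome ICC, the half case gives 9% and 18%.

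**A second parameterisation (simulation, total outcome ICC .06, .15 and .30, Fidelity at Level 2).** The table gives false-positive rates by group-level correlation between attendance and symptoms.

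| Attendance ICC | correlation .5 | correlation .8 |
|---|---|---|
| .05 | 6-7% | 8-9% |
| .15 | 9-11% | 16-20% |
| .30 | 15-17% | 31-39% |

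- With correlation 0, the rate is 4.3-5.9%.
- With the random attendance slope included (correlation .8, 150 replicates), it is 12% at attendance and outcome ICC .15, and 33% at .30 and .15.
- With Fidelity correlated .6 with the group attendance component (correlation .8), three settings give 12.5%, 23% and 20.5%.

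**After centring and adding group-mean attendance.** The rate is 3.7-6.5% in every 40-group random-intercept setting of the second parameterisation and 2.0-5.4% with the random slope. The mean coefficient is about zero.

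**The case against.** The strongest objection is that Aim 3 extends the Aim 2 models, which carry country and setting. Those are the only sources of between-group attendance variation that the plan names. A reader might infer that a country or urban-rural difference will be reported as an attendance effect. The documents do not support that: if the terms are carried over, that route is closed. What stands against the objection is that the displayed Aim 3 equations contain neither term, so the carry-over is ambiguous. Other group-level differences would also remain, for instance between the three-counselor teams that section 3C3b assigns at random to groups. No passage links such differences to attendance, so this is a possibility and not a documented fact.

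Second, the equations are schematic: they use a generic covariate term and one symbol for three coefficients. That the plan prescribes raw attendance is an inference from the absence of any centring statement. They are nevertheless the only Aim 3 specification given.

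Third, the size is assumed. Pilot attendance was high (section 3C1d: averages of 11 for children and 10.5 for guardians out of 12), which suggests limited spread. A reader who puts V = ICCy into the formula for the high case would get 54%. That figure should not be used. If .05 is the total outcome ICC, attendance alone would need group variance .25 x .3 = .075, a correlation of sqrt(.075/.05) = 1.22, which is impossible. If .05 is residual, the formula overweights between-group information and the rate is about 38%.

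**Conclusion.** The point holds as a conditional weakness of specification. The example model yields one attendance slope that mixes two associations. It can produce a false individual-level effect if group-mean attendance is related to group-level symptoms beyond Fidelity and any retained country and setting terms. Without that relation, the error rate stays nominal.

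The size rests on an attendance ICC and a group-level slope that the documents do not give. The range above therefore illustrates the mechanism and does not predict what this trial will show.

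The consequence is limited. Aim 3 is an exploratory, non-randomised analysis within one arm. A reader might infer that the effectiveness result is at risk; it is not, because the TF-CBT versus usual care comparison under Aim 1 does not use attendance. This is a worthwhile clarification of low severity.

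**What to change.** In the Aim 3 text and equations:

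1. Enter attendance at Level 1 as the deviation from its group mean.
2. Add group-mean attendance beside Fidelity in the Level 2 intercept equation.
3. Show explicitly that the Aim 2 country and setting terms are kept.
4. State that the Level 1 term is the within-group association and the Level 2 terms are group associations.

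No new data are needed. The individual term loses some precision because it no longer borrows between-group information. In the random-intercept calculation above, its SE becomes 1/sqrt(40W): .063 instead of .058 in the low case, and .070 instead of .060 in the high case. Level 2 gains group-mean attendance, plus country and setting if they were not already meant to be there. The design implies 40 groups, while section 3C5c counts 20 clusters; reconcile these when judging how many Level 2 terms are affordable.

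Centring removes group-level confounding only. Children who attend more may differ in other ways from others in their group, so the Level 1 term should still be reported as an association.

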We propose a RCT of TF-CBT that builds on our feasibility study, with the goal of testing the effectiveness of an intervention that is locally feasible, acceptable, and holds promise for improving mental health outcomes and functioning of orphaned children. Although 8 RCTs of TF-CBT have been conducted in the US, there has never been a RCT of its effectiveness in LAMICs with high prevalence of HIV. The proposed trial, to be conducted in both Moshi, TZ and Bungoma, KE ($N = 640$, with 20 TF-CBT groups provided in each region), includes: (1) a usual care control group in each region, (2) independent research interviewers; and (3) enhanced ecological validity and local responsibility by including the lay counselors from the feasibility study to assist [name] and [name] in training and supervising the lay counselors.

3C2a. Outcomes Examined. We plan to examine clinical outcomes, which include CTG, PTS, PTSD, depressive symptoms, behavioral problems, as well as any effect on the child-guardian relationship and the child's overall daily functioning (the last of these is a tool to be developed locally in the first quarter of the study; see Tables 3 & 4). We also plan to describe and examine the impact of implementation factors (e.g., TF-CBT fidelity, lay counselor knowledge gain, guardian and child attendance) on clinical outcomes. With the increasing attention given to task-shifting approaches³² and their promise for reducing the mental health treatment gap, implementation efforts that incorporate feasible methods for building greater local responsibility and sustainability are needed.

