The proposed study is a rigorous test of clinical outcomes building on a training and supervision approach employed by [name] (consultant on this study)^{33,34}, [name]^{35,76}, and others³⁵ in RCTs in other LAMICs. This approach involves local, trained lay individuals (i.e., our feasibility study lay counselors) who act as the direct treatment model supervisors, under supervision themselves, by TF-CBT and mental health experts (i.e., [name] & [name]). Our team views this RCT as the first step in a broader research plan to test the effectiveness of TF-CBT in successive implementation stages that systematically increase local expertise and responsibility and decrease expert involvement, with the goal of enhancing our knowledge around effective, feasible, and sustainable implementation strategies in LAMICs. As stated in the recently released NIH/PEPFAR RFA, focused on HIV/AIDS specifically (i.e., RFA-AI-11-003): "scientific advances regarding the implementation of effective interventions have not kept pace."

3C2b. The comparison group for the RCT is a "usual care" (UC) condition (i.e., existing orphan support services; (see Section 3C3c for our preliminary studies on UC in TZ & KE; also see Human Subjects). We enroll 320 child-guardian dyads in each of the two conditions (TF-CBT & UC; 640 total), with half of the participants enrolled in TZ and half in KE (see Table 2). Both sites are mixed urban and rural areas, allowing testing of TF-CBT in both settings to examine any impact of setting variables (i.e. differences in UC; urban vs. rural) on clinical outcomes or implementation (e.g., fidelity, attendance). Equal numbers of males and females, and children in age groups 7-10 and 11-13 will be recruited for both TF-CBT and UC. In the POFO study we easily recruited nearly twice this number (e.g., 560) in each region, indicating that the population of OAC in the areas in which we plan to recruit are high enough to support the proposed sample.

Sample size estimates for the RCT were determined using effect sizes from TF-CBT RCTs conducted in the US^{81,104}, from outcomes obtained in our TZ feasibility trial, and data from the Zambia TF-CBT feasibility trial (see Section 3C5b; for Power Analyses). Each site has a local UC group to enhance internal validity, given unique cultural, historical, political, religious, and ethnic differences, including relatively recent election riots experienced in KE.

	Moshi, TZ		Bungoma, KE	
	Urban	Rural	Urban	Rural

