[^] C= Child, G=Guardian, LC=Lay Counselor; RC: Research Coder (i.e., Data entry person) [*] BL = Baseline; 12w = 12-14 weeks; 6M = 6 months; 12M = 12 months [#] Post-T = Post-Training; Post C1: after delivery of one 1 cycle of groups (2 groups); Post C2: after delivery of 2 nd cycle of groups [†] Measure used in the TF-CBT for CTG Feasibility Study ⁺ Measures used in POFO (both TZ and KE)			

3C5. Data Analysis Plan

Basic data screening procedures will be conducted (e.g., means, standard deviations, skewness, plotting relationships) to screen for errors and explore normality, linearity, form, and outliers. Data will be transformed as appropriate. We will confirm the assumption of randomization at baseline by testing cohort differences in outcome variables (i.e. symptoms), history of traumatic events and basic demographics (i.e. gender and age). Minor differences will be controlled for in statistical models as described below. Statistical analyses for the main aims will be conducted using the SPSS¹¹⁸, Stata¹¹⁹ and Multilevel/Hierarchical Level Modeling¹²⁰ (MLM/HLM) software programs. HLM allows for the presence of missing data at Level 1 (such as when participants are lost to follow-up) appropriately adjusting for data missing at random, particularly when covariates associated with missingness are included in the statistical model¹²¹.

3C5a. Overview of Modeling Approach. Hypotheses related to Aim 1 will be tested using MLM (i.e. HLM, random coefficient models, mixed effects models), which are a powerful and flexible class of analytic approaches that allow for the analysis of non-independent data. MLM allow researchers to account for nesting within different data structures and to explicitly model effects across nested groups. For the current study, the outcome data will be observations of clinical outcomes at multiple time points, nested within children, who are also nested within TF-CBT groups (for the TF-CBT condition). Not accounting for the fact that some children are treated in the same treatment group, for example, could lead to biased estimates. The MLM approach reduces Type I errors caused by violating assumptions of independence, allows time-varying assessments and increases power by utilizing information from multiple time points in a single model.

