3C5c Power. Power analyses were conducted using Optimal Design 2.0¹²⁴. A primary concern when estimating power in HLM focuses on the Interclass Correlation Coefficient (ICC) for providers, as providers are nested within conditions. Higher positive ICCs result in less statistical power, and few estimates of provider ICCs for fidelity to treatment are available. A review of 20 studies predicting client functioning found provider ICCs clustering from -0.1 to .06¹²⁵. Because precise estimates for ICCs are unknown, we examined ICC thresholds within a range of effect sizes (with .05 Type I error rate, power of .80, 8 children per TF-CBT group; 320 children total). Estimates did not include the effect of covariates which, if moderately correlated with the outcome variable, will increase statistical power. Therefore, these estimates present a conservative estimate. Our primary hypothesis test (i.e. differences at 12-weeks between TF-CBT & UC) is sufficiently powered ($1-\beta = .80$) to detect small effects (.35) with ICCs up to .15, moderate effects (.50) with ICCs up to .30, and all conceivable large effects. For detecting condition differences in terms of the linear or quadratic slope, analyses suggested that the proposed *N* has power ($1-\beta = .80$) to detect effects as small as .29 on slopes. Finally, for Aim 3, the current sample of 320 individuals in the TF-CBT condition, the current study is sufficiently powered to detect small (.21) effects of individual implementation variables on outcomes, but with only 20 clusters (i.e., groups) the study will have less power to detect all but large effects of group-level variables (e.g., fidelity).

3C6. Rationale of Choices Made in the Research Design. Our team carefully considered various design and methodological challenges, our rationale for various decisions is discussed here.

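### The power statement for the primary 12-week test does not describe the planned trial: it prints 320 children in total, while the design has 640 with grouping in the TF-CBT arm only

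*Combined protocol and SAP*

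**What the plan says.** Section 3C5c (Power) sets out its basis as "with .05 Type I error rate, power of .80, 8 children per TF-CBT group; 320 children total", using Optimal Design 2.0 and no covariates. It then states that the primary test, TF-CBT against UC at 12 weeks, has adequate power "to detect small effects (.35) with ICCs up to .15, moderate effects (.50) with ICCs up to .30". It does not say whether the test is one- or two-sided, which SD standardises the effect, or how many clusters were entered.

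The design sections give other inputs. Section 3C2b says "We enroll 320 child-guardian dyads in each of the two conditions", which makes 640, and Table 2 agrees. Section 3C2 plans the trial "with 20 TF-CBT groups provided in each region". With two regions that is 40 groups, and 40 × 8 = 320 TF-CBT children. Section 3C5a describes children as "nested within TF-CBT groups (for the TF-CBT condition", and the 12-week model in 3C5b likewise accounts for clustering in that arm only. UC children belong to no group.

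**The concern.** Section 3C5c is the only place where the plan says what its primary test can detect. Its printed total is half the planned enrolment, and nothing in it shows that one arm is grouped and the other is not. A reader who repeats the calculation from the printed inputs would find the trial short of power. A reader who takes the printed thresholds at face value would think the design can detect no less than .35 to .50. Neither is right for the trial as planned. The true margin matters for judging how much loss to follow-up the design can bear, for which the paragraph states no allowance, and for planning around the several Aim 1 outcomes.

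**Working it through.** **Inputs.** Alpha .05 (two-sided assumed), target power .80, 8 children per group and no covariates, all from 3C5c. The planned 320 per arm is from 3C2b, the 40 groups from 3C2, and clustering in TF-CBT only from 3C5a and 3C5b. Effects are in total-SD units unless stated. ρ is the ICC. Power comes from the noncentral t (or F) distribution.

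**Formulas.**
- Both arms clustered, J clusters of 8 in all: Var = 4[ρ + (1 − ρ)/8]/J, df = J − 2.
- Only TF-CBT grouped, n per arm: Var = (1 + 7ρ)/n + 1/n. The df are either the number of groups minus 1, or Satterthwaite. Where two figures are given, they reflect this choice.

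**Step 1: the plan's figures on its printed basis (320 in total).**
- Both arms clustered, J = 40. At ρ = .15, Var = 4(.15 + .10625)/40 = .02563, SE = .160, and .35/.160 = 2.19, so power is .57. At ρ = .30, Var = 4(.30 + .0875)/40 = .03875, SE = .197, and .50/.197 = 2.54, so power is .70. The ICC limits for 80% power are .03 (effect .35) and .20 (effect .50).
- Only TF-CBT grouped, 20 × 8 against 160. At ρ = .15, Var = (2.05 + 1)/160 = .01906, SE = .138, ratio 2.53, power .67 to .70. At ρ = .30, Var = (3.10 + 1)/160 = .02563, SE = .160, ratio 3.12, power .84 to .86.

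On this basis the .35 claim fails under both layouts. The .50 claim fails only if both arms are clustered.

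**Step 2: the planned design (40 × 8 against 320 ungrouped).**
- ρ = .15: Var = 3.05/320 = .00953, SE = .0976, .35/.0976 = 3.59, power about .94.
- ρ = .30: Var = 4.10/320 = .01281, SE = .1132, .50/.1132 = 4.42, power about .99.
- ICC limit for .35: .39 to .41, against the printed .15.
- Detectable effect at ρ = .15, Satterthwaite df 84: (1.99 + .85) × .0976 = .28. In the same way, .24 to .25 at ρ = .05 and .32 to .33 at ρ = .30.

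**Step 3: sensitivity to assumptions the plan leaves open.**

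| Layout (two-sided .05) | Power (.35, .15) | Power (.50, .30) | Detectable at ICC .15 | Detectable at ICC .30 |
|---|---|---|---|---|
| 40 × 8 vs 320, equal total variance | .94 | .99 | .28 | .32–.33 |
| 40 × 8 vs 320, group variance added in TF-CBT only | .91–.92 | .96–.97 | .29–.30 | .37 |
| 18 counselors (320/18 = 17.8 children each) vs 320 | .79–.81 | .89–.90 | .35 | .43–.44 |
| 640 with both arms clustered, J = 80 | .86 | .94 | .32 | .40 |
| 40 × 6.4 vs 256 (20% loss, an assumption) | .90–.91 | .98–.99 | .30 | .34 |

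In the second row, Var = [1 + 8ρ/(1 − ρ)]/320 + 1/320 with the UC SD as the unit. At ρ = .15 this is (2.41 + 1)/320 = .01066. There the ICC limit for .35 is about .26 and for .50 about .49. The third row treats counselors as simple clusters, which only approximates counselors rotating across groups in threes (3C3b).

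**The case against.** Four arguments can be made for the printed text.

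- **The claims are lower bounds.** Sufficient power for ICCs up to a value does not mean exactly .80 at that value. With 640 children both claims are true, whether both arms are treated as clustered (.86 and .94) or only TF-CBT (.94 and .99). This stands.
- **The figure of 320 may mean the TF-CBT arm.** The Aim 3 sentence of the same paragraph uses 320 for that arm. On this reading the claims hold and the fault is unclear wording. This is possible, but the text calls the number a total and does not mention the UC children.
- **Some layouts come close to the printed thresholds.** Eighty clusters of 8, with the effect in within-group SD units, give ICC limits of .152 and .332. The paragraph also speaks of provider ICCs, and 18 counselor clusters give a limit of about .15 to .16 for .35. A reader might therefore infer too much in saying that the thresholds fit no version of the design. But the first layout puts UC children in groups that do not exist and needs an SD the plan does not define. The second is not the group clustering modelled in 3C5b.
- **Sidedness is not stated.** At one-sided .05, the printed total gives about .79 to .81 for (.35, .15) with only TF-CBT grouped, which is borderline, and .69 with both arms clustered.

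These arguments limit the point to one of description and traceability. They do not make the printed basis agree with the planned trial.

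**Conclusion.** The point holds as a correction to a stated power figure. If 320 is the whole sample, the .35 claim fails at two-sided .05 (power .57, or .67 to .70). For the planned 640 children with grouping in TF-CBT only, power is about .94 and .99, and the ICC limit for .35 is about .4 rather than .15. These figures assume independent groups of 8, no losses and equal total variance in the two arms. With group variance added in TF-CBT only, power is still above .90 at both printed pairs.

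A reader might infer that the trial is underpowered. The documents do not support that: for the planned group layout the error is on the safe side. The margin is thin only if counselors are taken as the cluster unit, where (.35, .15) sits at about .80. A reader might also take the recomputed figures as effects that a null result would rule out. They are not: a detectable effect is a planning quantity, and a null result is read from its confidence interval.

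**What to change.** Rewrite the primary-test part of 3C5c:

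- State 640 children, 40 TF-CBT groups of 8 against 320 ungrouped UC children, with clustering in the TF-CBT arm only.
- State the sidedness of the test, the SD that standardises the effect, and the cluster unit (group or counselor).
- Report detectable effects at 80% power with their variance assumption: about .24, .28 and .32 to .33 SD at group ICC .05, .15 and .30 with equal total variance, and about .30 and .37 at ICC .15 and .30 if group variance adds only in TF-CBT.
- Add a counselor-level sensitivity with 18 providers (about .35 at ICC .15), noting that simple nesting is an approximation.
- Show any allowance for loss as an assumption. With 20% loss, for example, the equal-variance figures become about .27, .30 and .34.
- Reconcile the count of 20 clusters in the Aim 3 sentence with the 40 planned groups while the paragraph is open.

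The cost is one paragraph. Sample size, conduct and the primary analysis stay as they are.
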